Common causes of fatigue, such as anemia, deconditioning, emotional distress (depression and/or anxiety), poor nutrition, dehydration, sleep disturbance, and hypothyroidism should be ruled out and treated according to standard of care. Pharmacological management should be considered after disease specific morbidities have been excluded when not prohibited.

Weight Loss

Anorexia and weight loss should be managed according to local standard of care including nutritional support. Pharmacologic therapy should be considered for appetite enhancement when not prohibited by a particular protocol.

Corrected QT Prolongation

The effect of orally administered cabozantinib 140 mg qd on QTc interval was evaluated in a placebo-controlled study in subjects with MTC. A mean increase in QTcF of 10-15 ms was observed after 4 weeks after initiating cabozantinib treatment. A concentration-QTc relationship could not be definitively established. Changes in cardiac wave form morphology or new rhythms were not observed. No cabozantinib-treated subjects in this

study had a QTcF > 500 ms. Review of the larger safety database (~5000 subjects exposed to cabozantinib in clinical trials and in post-marketing experience) confirmed the absence of safety concerns associated with QT prolongation. There were no events of torsades de pointes reported.

Concomitant treatment with strong cytochrome P450 (CYP) 3A4 inhibitors, which may increase cabozantinib plasma concentrations, should be avoided.

If at any time on study there is an increase in QTcF to an absolute value > 500 ms, two additional ECGs must be performed with intervals not less than 3 min apart within 30 min after the initial ECG.

If the average QTcF from the three ECGs is > 500 ms, the following actions must be taken:

- Interrupt cabozantinib treatment
- Hospitalize symptomatic subjects (eg, with palpitations, dizziness, syncope, orthostatic hypotension, a significant ventricular arrhythmia on ECG) for a thorough cardiology evaluation and management
- Consider cardiology consultation for asymptomatic subjects for evaluation and management
- Check electrolytes, especially magnesium, potassium and calcium; correct abnormalities as clinically indicated
- Check concomitant medications for any medication that may have contributed to QT prolongation, and if possible, discontinue these medications (http://www.qtdrugs.org)

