- Repeat ECG triplicates hourly until the average QTcF is ≤ 500 msec, or otherwise determined by consultation with a cardiologist or appropriate expert.

Subjects with QTc prolongation and symptoms must be monitored closely until the QTc elevation and symptoms have resolved. Cabozantinib treatment may be restarted at a reduced dose level if all of the following conditions are met:

- Symptoms are determined to be unrelated to the QT interval prolongation
- The QTcF value > 500 ms is not confirmed
- Cabozantinib treatment has been interrupted through a minimum of 1 week following the return of the QTcF to ≤ 500 ms.
- QT prolongation can be unequivocally associated with an event other than cabozantinib administration and is treatable/has been resolved

Following reinitiation of study treatment, ECGs must be done as clinically indicated. Cabozantinib treatment must be permanently discontinued if either of the following applies:

- Cardiac evaluation confirms that symptoms are the consequence of QT interval prolongation
- Recurrence of QTcF prolongation after reinitiation of study treatment at a reduced dose

Electrolyte Disorders

Serum electrolyte disorders including hyponatremia, hypokalemia, hypomagnesemia, and hypophosphatemia have been reported during treatment with cabozantinib, and serum electrolyte levels should be monitored frequently while receiving cabozantinib. Clinically relevant electrolyte disorders should be managed according to the dose modification guidelines as outlined in Section 4.2 or as clinically indicated. Standard clinical practice guidelines should be used for management of electrolyte disorders and may include oral or intravenous replacement.

CONFIDENTIAL

Endocrine Disorders

Treatment-emergent elevation of thyroid-stimulating hormone (TSH) has been observed with cabozantinib treatment. Currently available data are insufficient to determine the mechanism of thyroid function test alterations and its clinical relevance. Management of thyroid dysfunction (eg, symptomatic hypothyroidism) should follow accepted clinical practice guidelines.

Angioedema

Angioedema should be managed according to standard practice. The subject should be observed until symptoms resolve, with particular attention to maintaining an open airway.

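### Section 4.4: the QTc restart condition turns on an undefined word and, on its natural reading, contradicts the trigger for interruption

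*Combined protocol and SAP*

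**What the plan says.** The text is in Section 4.4, under Corrected QT Prolongation.

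- **Verification.** After one QTcF above 500 ms on study, "two additional ECGs must be performed with intervals not less than 3 min apart within 30 min after the initial ECG".
- **Trigger.** "If the average QTcF from the three ECGs is > 500 ms, the following actions must be taken". The first action is "Interrupt cabozantinib treatment". The last is "Repeat ECG triplicates hourly until the average QTcF is ≤ 500 msec", unless a cardiologist or other expert determines otherwise.
- **Restart.** After a sentence on close monitoring of subjects who have both prolongation and symptoms, the section says: "Cabozantinib treatment may be restarted at a reduced dose level if all of the following conditions are met". The four conditions are: (1) the symptoms are judged unrelated to the prolongation; (2) "The QTcF value > 500 ms is not confirmed"; (3) "Cabozantinib treatment has been interrupted through a minimum of 1 week following the return of the QTcF to ≤ 500 ms"; (4) the prolongation clearly has a cause other than cabozantinib that is treatable or has resolved.
- **Permanent discontinuation.** There are two grounds: cardiac evaluation attributes the symptoms to the QT interval, or "Recurrence of QTcF prolongation after reinitiation of study treatment at a reduced dose".

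Section 4.6 lists a treatment hold of more than 28 days among the events that end therapy. For eligibility, Section 3.2.11 settles a reading above 500 ms by the average of three ECGs.

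**The concern.** The patient for whom a restart rule is needed has been interrupted because the triplicate average was above 500 ms. One restart condition asks that the value above 500 ms was not confirmed. Taken at face value, entry to the rule and exit from it require opposite facts.

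An investigator who applies all four conditions keeps the patient on hold. One who treats the second condition as a drafting slip restarts at a reduced dose. The same patient would be managed differently under the same text, in a cardiac safety instruction, and with different cabozantinib exposure. This can happen between investigators at one site. It can also happen between sites, if there are any: the study summary says single center, while Sections 5.2 and 10.3 provide for participating sites.

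**Working it through.** The plan states no figure on this point, so the check is one of logic.

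**Step 1: the natural reading.** Let C mean that the average QTcF of the three ECGs is above 500 ms. In Section 4.4 that average is the step that decides what follows a single high reading, and Section 3.2.11 uses the same step for eligibility. So read *confirmed* as C.

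- Mandatory interruption requires C to be true.
- Restart condition 2 requires C to be false.
- Mandatory interruption followed by restart requires C and not-C, which no patient can satisfy.

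**Step 2: the neighbouring text.** Condition 3 speaks of QTcF returning to 500 ms or less, and condition 4 of a prolongation that has another cause. Both presuppose a real prolongation. The second ground for permanent discontinuation presupposes that some patients restart. If C is false, the QTc rule requires no interruption, so the one-week wait in condition 3 has no mandatory hold to act on.

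**Step 3: where the patient ends up.** Take C true and no symptoms attributed to the QT interval.

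- Restart is not allowed, because condition 2 fails.
- Neither ground for permanent discontinuation applies: there are no QT-caused symptoms, and no restart after which prolongation could recur.
- The hold therefore runs until the 28-day limit in Section 4.6. This assumes that the limit applies to a hold of cabozantinib alone. Section 4.6 does not name the agent, and Section 4.2 lets the two agents be modified independently.

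**Step 4: other meanings of *confirmed*.** None of these is stated in the protocol.

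- *The two repeat ECGs alone.* With illustrative readings of 530, 490 and 490 ms, the average is (530 + 490 + 490) / 3 = 1510 / 3 = 503.3 ms. Interruption is mandatory although neither repeat exceeds 500 ms, so condition 2 can be met.
- *A later hourly triplicate.* Condition 2 can be met once the average has fallen, but it then adds little to condition 3, which already requires that fall.
- *Cardiology review.* Condition 2 can be met, but the criterion would be the reviewer's own.

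**Step 5: how often it matters.** The documents give no event rate. Section 1.2 reports no confirmed QTcF above 500 ms in a study at 140 mg or in the renal cell study at 60 mg, and this trial starts at 40 mg. Section 4.4 cites about 5000 exposed subjects without a QT safety concern. Against that, Section 3.2.11 excludes only values above 500 ms, so a patient may enter close to the threshold. Section 5.5 repeats the ECG at weeks 3, 6 and 9 and then every 4 to 6 weeks.

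**The case against.** The strongest reply is that the rule is not impossible to follow. A reader might infer that no interrupted patient can ever restart and that every such patient is permanently off cabozantinib. The documents do not support that, for four reasons.

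- The trigger is an average, not three readings each above 500 ms. *Confirmed* is undefined, and under the meanings in Step 4 the four conditions can be met together.
- The average makes interruption mandatory, but Section 4.4 also says generally that interruptions should be considered for adverse events. After a precautionary hold on one high reading with a triplicate average at or below 500 ms, condition 2 is met. The recurrence rule could refer to restarts of that kind.
- The restart sentence follows one about symptomatic subjects, and its first condition concerns symptoms. Whether the list governs asymptomatic patients is unclear.
- A confirmed value above 500 ms is not itself a ground for permanent discontinuation. The literal result is a hold, ended if at all by another rule.

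It can be added that the event is rare and that the literal reading withholds drug rather than giving it.

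All of this stands as a limit on the claim, but it does not remove the defect. The rule works for a mandatory interruption only if the investigator supplies a definition that the protocol lacks. Rarity bears on how many patients are affected, not on whether the instruction can be followed when it is needed.

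**Conclusion.** The point holds in a limited form. Section 4.4 leaves *confirmed* undefined. If it means the triplicate average, the only verification step given, the restart list contradicts the trigger for every mandatory interruption, and no other section repairs this. A patient without QT-caused symptoms is then left between two lists, neither able to restart nor named for permanent discontinuation.

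This rests on that reading of *confirmed*, on the list applying to the patient in question, and, for the 28-day end point, on Section 4.6 covering a hold of cabozantinib alone. It does not show that restart is impossible in every case, or that the protocol orders a permanent stop.

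Few of up to 27 patients are likely to be affected, possibly none. The PFS-6 hypotheses, type I error and power do not change. The point is still worth correcting, because this is a mandatory cardiac safety instruction that misfires on its most natural reading.

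**What to change.** Reconcile the trigger and the restart list in Section 4.4 under Corrected QT Prolongation. The amended text should:

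- define *confirmed*, by reference to the triplicate average or to whatever other step is meant;
- state which conditions apply after a confirmed value and which after an unconfirmed one;
- say whether the conditions are joint or alternative;
- say whether the list covers asymptomatic patients;
- say what happens to a patient who meets neither the restart list nor the permanent-discontinuation list, and how the 28-day limit in Section 4.6 applies to a hold of cabozantinib alone.

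The sponsor must decide the clinical rule; this review takes no position on it. The cost is a wording amendment of about one paragraph, with the approvals that Section 10.7 requires. Sample size, data collection and analysis do not change.

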4.5 Concomitant Medications/Treatments

Cabozantinib

Strong CYP3A4 Inhibitors

Coadministration of a cabozantinib capsule formulation with a strong CYP3A4 inhibitor increased the exposure of cabozantinib, which may increase the risk of exposure-related adverse reactions. Avoid coadministration of CABOMETYX with strong CYP3A4 inhibitors. Reduce the dosage of CABOMETYX if coadministration with strong CYP3A4 inhibitors cannot be avoided. Avoid grapefruit, grapefruit juice, star fruit and Seville oranges which may also increase exposure of cabozantinib.

Strong CYP3A Inducers

Coadministration of a cabozantinib capsule formulation with a strong CYP3A4 inducer decreased the exposure of cabozantinib, which may reduce efficacy. Avoid coadministration of CABOMETYX with strong CYP3A4 inducers. Avoid St. John's Wort which may also decrease exposure of cabozantinib.

Pembrolizumab

Glucocorticoids

Steroids in excess of a daily dose of 10mg prednisone equivalent have to be avoided due to immunosuppressive effects which can counteract the efficacy of pembrolizumab.

Thalidomide Analogues

Pembrolizumab may enhance the adverse/toxic effect of Thalidomide Analogues. Specifically, mortality may be increased when this combination is used for treatment of refractory multiple myeloma. Avoid combination.

4.6 Duration of Therapy

In the absence of treatment delays due to adverse events, treatment may continue until:

- Disease progression as defined radiographic progression by RECIST v1.1 criteria OR death OR symptomatic progression as clinically determined by the treating physician
- Inter-current illness that prevents further administration of treatment
- Unacceptable adverse event(s)
- Treatment held for more than 28 days
- Patient decides to withdraw from the study, OR
- General or specific changes in the patient's condition render the patient unacceptable for further treatment in the judgment of the investigator.

4.7 **Duration of Follow Up**

Patients will be followed every 3 months until death or 18 months after the last patient is enrolled, whichever occurs first. Patients removed from treatment for unacceptable adverse events will be followed until resolution or stabilization of the adverse event. Follow-up after removal from treatment is every 3 months (either clinic visit or phone call).

4.8 Removal of Patients from Protocol Therapy

Patients will be removed from therapy when any of the criteria listed in Section 5.6 apply. Notify the Principal Investigator via email ([contact] and [contact]), and document the reason for study removal and the date the patient was removed in the Case Report Form. The patient should be followed-up per protocol.

4.9 **Patient Replacement**

Patients will not be replaced

5.0 STUDY PROCEDURES

Telemedicine Visits

In-person visits are the preferred study visit method for collection of the assessments and procedures. Study visits conducted by phone or videoconferencing technology (i.e., "virtual" or "telemedicine" visits), including adverse event assessments for patients, may be substituted for protocol-required in-person visits, if the site investigator determines that the phone/virtual visit is adequate to achieve the central purpose of the visit.

5.1 Screening/Baseline Procedures

Assessments performed exclusively to determine eligibility for this study will be done only after obtaining informed consent. Assessments performed for clinical indications (not exclusively to determine study eligibility) may be used for baseline values even if the studies were done before informed consent was obtained as long as these assessments are completed within 28 days prior to registration.

All screening procedures must be performed within 28 days prior to registration unless otherwise stated. The screening procedures include:

5.1.1 Informed Consent

5.1.2 Screening Confirmation

Patient information should be entered into Oncore within 1 business day of consent. Sites are responsible for assigning subject ID. Sites will be assigned a unique site code. Subject IDs should follow a format with the unique site code followed by the sequential patient ID. For example, Site Code-Sequential Number (i.e. for UCI's first patient the subject ID will be 01-01). (Refer to Oncore SOP for Oncore data entry instructions)

5.1.3 Medical history

Complete medical, oncology and surgical history, history of infections

5.1.4 Demographics

Age, gender, race, ethnicity

5.1.5 Review subject eligibility criteria

5.1.6 Review previous and concomitant medications

5.1.7 Physical exam

5.1.8 Vital signs

Temperature, pulse respirations, blood pressure, height, and weight (height only at screening)

5.1.9 ECOG Performance status

5.1.10 Hematology

Complete blood count with differential (CBC)

5.1.11 Serum chemistries

Comprehensive metabolic panel (CMP) to include: albumin, alkaline phosphatase, ALT/SGPT, AST/SGOT, BUN, creatinine, hemoglobin, electrolytes (sodium, potassium, calcium, chloride, bicarbonate), glucose, TSH, fT3, fT4, total bilirubin, urine protein/creatinine ratio, PT/INR and PTT,.

Tumor Markers (Optional)

Carcinoembryonic antigen (CEA) and cancer-related antigen 19-9 (CA 19-9).

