4.4 Cabozantinib adjustment for toxicity

The most frequent AEs experienced by ≥ 20% of subjects treated with cabozantinib in descending order of frequency were diarrhea, fatigue, decreased appetite, nausea, weight decreased, PPES, vomiting, constipation, hypertension, dysgeusia, dysphonia, asthenia, and dyspnea.

Subjects may also experience other medically important but less frequent AEs including arterial thrombotic AEs (e.g., deep vein thrombosis [DVT], pulmonary embolism, transient ischemic attack [TIA], and myocardial infarction [MI], severe hemorrhagic events, proteinuria, wound healing complications, gastrointestinal (GI) perforation, abscesses including intra-abdominal and pelvic abscess, GI and non-GI fistula formation, osteonecrosis, and reversible posterior leukoencephalopathy syndrome (RPLS).

Adverse events associated with laboratory abnormalities experienced by ≥ 5% of subjects treated with cabozantinib in descending order of frequency were anemia, AST increased, ALT increased, hypothyroidism, hypokalemia, hypomagnesemia, thrombocytopenia, hypocalcemia, hypophosphatemia, lactate dehydrogenase (LDH) increased, lipase increased, neutropenia, hyponatremia, ALP increased, hyponatremia, and leukopenia.

Many adverse events may occur early (within the first few weeks) in the course of treatment with cabozantinib, as cabozantinib is expected to reach steady state exposure at approximately 2 weeks following first dose. Events that generally have an early onset include hypocalcemia, hypokalemia, thrombocytopenia, hypertension, PPES, abdominal pain, mucosal inflammation, constipation, diarrhea, and vomiting.

Adverse events should be managed with supportive care at the earliest signs of toxicity. Dose reductions and treatment interruptions should be considered. Dose reductions are recommended for events that, if persistent, could become serious or intolerable (Section 4.2).

Cabozantinib should be discontinued for the following AEs: visceral perforation or fistula formation, severe hemorrhage, serious arterial thromboembolic events, nephrotic syndrome, hypertensive emergency, persistent uncontrolled hypertension despite optimal medical management, and reversible posterior leukoencephalopathy syndrome (RPLS).

Gastrocintestinal Disorders

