5.5 Time and Events Table

Baseline evaluations are to be conducted within 1 week prior to administration of protocol therapy. Scans and x-rays must be done ≤4 weeks prior to the start of therapy. In the event that the patient's condition is deteriorating, laboratory evaluations should be repeated within 48 hours prior to initiation of the next cycle of therapy.

	Baseline -28 to -1 days	C1D1 +/- 3 days	At every cycle (21 days) +/- 3 days	q 8 Weeks for first year, q 3 months after the first year +/- 1 week	Off Treatment	Follow- up (q 3 months until death or up to 18 months after last patient is enrolled, whicheve r occurs first) +/- 14 days
Assessment						
Informed Consent	Χ					
History and PE	Χ	Х	X		X	
Concomitant Medications	Х	Х	Х		X	
Performance Status	Х	Х	Х		Х	
Adverse Events	X**	Х	Х		Х	
Tumor Measurements	Х			Х		
CT CAP or CT chest/MRI Abd/Pelvis	Х			Х		
CBC / CMP / UA / UPCR	Х	X	Х		Х	
PT/INR, PTT	Х	Х	X***			
TFTs (TSH, free T3, free T4)	Х	Х	X***			
CEA and CA 19-9 (optional)****			Х			
12-lead ECG	Х	Χ	X***		Х	
Pregnancy Test*	Х	Х	X***		Х	
Review of systems						Х
Study Drug Accountability			Х		Х	

^{*}Urine or serum pregnancy test is done according to local institutional standard and should be obtained ONLY in women of child-bearing potential.

^{**} Only Serious Adverse Events will be assessed and reported during baseline

^{***} To be done Day 1 of Weeks 3, 6, 9 and then every 4-6 weeks

^{****} This is an optional component and should only be collected if done according to local

institutional standards.

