7.1.4 Adverse Reactions

Cabozantinib

>10%:

Cardiovascular: Hypertension (30% to 61%)

Central nervous system: Fatigue (41% to 56%), mouth pain (36%), voice disorder (19%), headache (11% to 18%), dizziness (11% to 14%)

Dermatologic: Palmar-plantar erythrodysesthesia (42% to 50%), hair discoloration (34%), skin rash (19% to 23%), xeroderma (11% to 19%), alopecia (16%), erythema (11%)

Endocrine & metabolic: Increased lactate dehydrogenase (84%), increased serum triglycerides (53%), hypocalcemia (8% to 52%), hypoalbuminemia (36% to 51%), hypophosphatemia (25% to 48%), weight loss (17% to 48%), hyperglycemia (37%), hypomagnesemia (19%)

CONFIDENTIAL

to 31%), hyponatremia (10% to 30%), increased gamma-glutamyl transferase (27%), hypokalemia (18% to 23%), hypothyroidism (8% to 21%)

Gastrointestinal: Diarrhea (54% to 74%), stomatitis (13% to 51%; grades 3/4: 2% to 5%), nausea (31% to 50%), decreased appetite (46% to 48%), dysgeusia (12% to 34%), vomiting (24% to 32%), constipation (25% to 27%), abdominal pain (23% to 27%), mucositis (14% to 19%), increased serum amylase (16%), dysphagia (13%), dyspepsia (10% to 12%)

Genitourinary: Proteinuria (2% to 12%)

Hematologic & oncologic: Lymphocytopenia (25% to 53%; grades 3/4: 1% to 16%), neutropenia (31% to 43%; 35%; grades 3/4: 2% to 7%), leukopenia (35%), thrombocytopenia (25% to 35%; grades 3/4: 1%), anemia (17% to 31%; grades 3/4: 1% to 5%)

Hepatic: Increased serum aspartate aminotransferase (73% to 86%), increased serum alanine aminotransferase (68% to 86%), increased serum alkaline phosphatase (35% to 52%), hyperbilirubinemia (25%)

Neuromuscular & skeletal: Asthenia (19% to 22%), arthralgia (11% to 14%), limb pain (9% to 14%), muscle spasm (8% to 13%)

Renal: Increased serum creatinine (58%)

Respiratory: Dyspnea (12% to 19%), cough (18%)

1% to 10%:

Cardiovascular: Hypotension (7%), venous thromboembolism (6% to 7%), syncope (grades 3/4: 5%), pulmonary embolism (4%), arterial thromboembolism (1% to 2%), vascular disease (grades 3/4: 1%)

Central nervous system: Anxiety (9%), paresthesia (7%), peripheral sensory neuropathy (7%), pain (grades 3/4: 5%), peripheral neuropathy (5%), depression (grades 3/4: 4%), confusion (grades 3/4: 1%)

Dermatologic: Hyperkeratosis (7%), dermal ulcer (grades 3/4: 3%)

Endocrine & metabolic: Dehydration (7%), hyperkalemia (grades 3/4: 1%)

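### The scheduled chemistry panel omits magnesium and phosphate, although Section 4.4 names low levels of both as cabozantinib toxicities to monitor; a footnote to the visit table also conflicts with Sections 5.3.1 and 5.1.11

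*Combined protocol and SAP*

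**What the plan says.** - **Section 4.4, Electrolyte Disorders:** "hyponatremia, hypokalemia, hypomagnesemia, and hypophosphatemia have been reported during treatment with cabozantinib", and "serum electrolyte levels should be monitored frequently while receiving cabozantinib". Clinically relevant disorders are to be managed under Section 4.2 or as clinically indicated. Earlier in 4.4, hypomagnesemia and hypophosphatemia also appear among the laboratory adverse events seen in at least 5% of cabozantinib-treated subjects.
- **Section 7.1.4:** for cabozantinib, "hypophosphatemia (25% to 48" percent, and hypomagnesemia 19% to 31%. No grade is attached to either figure, so both are read here as all-grade.
- **Section 5.1.11:** the chemistry panel includes "electrolytes (sodium, potassium, calcium, chloride, bicarbonate". Thyroid tests (TSH, fT3, fT4), PT/INR and PTT are listed in the same panel.
- **Section 5.3.1:** serum chemistries and, if applicable, a pregnancy test are due before each cycle.
- **Section 5.5 table:** CBC, CMP, urinalysis and UPCR are due at baseline, Cycle 1 Day 1, every 21-day cycle (±3 days) and off treatment. There is no magnesium or phosphate row.
- **Section 4.4, Corrected QT Prolongation:** once the average QTcF of three ECGs exceeds 500 ms, sites are told: "Check electrolytes, especially magnesium, potassium and calcium".
- **Section 5.5, triple-asterisk footnote:** "To be done Day 1 of Weeks 3, 6, 9 and then every 4-6 weeks". It is attached to the every-cycle entries for PT/INR and PTT, thyroid tests, ECG and pregnancy test.
- **Section 2.3:** rates of drug-related grade 3-5 adverse events are a secondary endpoint.

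**The concern.** The safety narrative and the data-collection schedule do not match. Section 4.4 tells sites to watch for four electrolyte disorders, but the required panel can detect only two of them. Low magnesium and low phosphate are laboratory findings, and a mild or silent case is seen only if someone orders the test. If ordering is left to local habit, ascertainment varies between clinicians and sites, and any error in the adverse-event rates runs in one direction, toward too few events. There would also be no scheduled baseline value against which to judge a later result, including the magnesium level requested after QT prolongation.

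The footnote raises a second, smaller problem. It sets one timetable for thyroid, coagulation and pregnancy tests, while Sections 5.1.11 and 5.3.1 together set another. A coordinator cannot tell which tests are due at which visit.

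**Working it through.** The protocol gives no figure to reproduce here. The check is a comparison of lists, visit-day arithmetic, and a conversion of the protocol's rates into patients.

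**1. Named disorders against the panel**

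| Disorder named in 4.4 | Analyte in the 5.1.11 panel? | Added by 5.3.1 or 5.5? |
|---|---|---|
| Hyponatremia | Sodium: yes | n/a |
| Hypokalemia | Potassium: yes | n/a |
| Hypomagnesemia | Magnesium: no | No |
| Hypophosphatemia | Phosphate: no | No |

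Of the three analytes singled out in the QT instruction, potassium and calcium are in the panel and magnesium is not.

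**2. Expected numbers of patients**

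Expected patients = number treated × rate, using the Section 7.1.4 cabozantinib rates. The totals are 27 (both stages) and 19 (first stage), from Section 9.2.

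- Hypophosphatemia, 27 patients: 27 × 0.25 = 6.8 to 27 × 0.48 = 13.0.
- Hypomagnesemia, 27 patients: 27 × 0.19 = 5.1 to 27 × 0.31 = 8.4.
- Hypophosphatemia, 19 patients: 19 × 0.25 = 4.8 to 19 × 0.48 = 9.1.
- Hypomagnesemia, 19 patients: 19 × 0.19 = 3.6 to 19 × 0.31 = 5.9.

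These are patients expected to have the abnormality at any grade. They are not a count of missed events or of grade 3-5 events.

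**3. Which days the footnote denotes**

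- Cycle visits: Day 1 of Cycle k = 1 + 21(k − 1), so Cycles 2, 3 and 4 start on Days 22, 43 and 64.
- Footnote read literally: Day 1 of Week w = 7(w − 1) + 1, so Days 15, 36 and 57. Each is 7 days before a cycle visit, outside the ±3-day window.
- Footnote read as after 3, 6 and 9 completed weeks: 7w + 1, so Days 22, 43 and 64. These are the cycle visits.

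**4. The interval after Week 9**

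Every 4 to 6 weeks is every 28 to 42 days, while Section 5.3.1 works on a 21-day cycle. At 42 days, the tests would fall on every second cycle. At 28 days, they would drift against the cycle visits. Under either reading in step 3, some cycles after Week 9 would start without tests that 5.3.1 requires: the pregnancy test where applicable, and the thyroid and coagulation tests that 5.1.11 counts as serum chemistries.

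**The case against.** Several counter-arguments have force.

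**No scheduled test is not the same as no detection.** The panel is introduced as a list of things to include, so a site may add to it. Section 4.4 itself asks for frequent electrolyte checks right after naming these disorders, and magnesium is requested after QT prolongation. Symptom-driven or locally ordered results can still be graded and can still lead to the Section 4.2 rules. This stands, and it limits the claim: events may be undercounted, but it would be wrong to infer that they cannot be recorded. It does not remove the gap, because nothing in the schedule requires the measurement.

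**The rates may not transfer.** Section 7.1.4 gives no dose for its figures. The large cabozantinib trials described in Section 1.2 used 60 mg daily, and this trial starts at 40 mg. Pembrolizumab has its own listed hypophosphatemia rate (19% to 29%), but the single-agent rates cannot be added. This also stands.

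**The footnote has a benign reading.** Weeks 3, 6 and 9 are multiples of the cycle length and sit in a column of cycle visits, so Days 22, 43 and 64 may well be intended. That is fair, and a separate Day 15 attendance should not be inferred. The later 4-6 week interval remains in conflict.

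A reader might draw two further inferences that the documents do not support:

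- *That the first repeat blood pressure, CBC and chemistry, at Day 22, comes too late.* Section 4.4 places many events in the first few weeks of treatment, and Day 22 falls there. Only steady state is put at about two weeks: "cabozantinib is expected to reach steady state exposure at approximately 2 weeks following first dose". The visit window of Days 19 to 25 is 4 to 10 days after Day 15. Checks every 21 days do not contradict the requests for regular blood pressure (7.1.2) and serial counts (4.4).
- *That testing on cycle days would generate repeated protocol violations.* Section 7.5 does give safety procedures missed at set times as an example of a violation, but only for violations as defined in Section 7.3.1. That definition requires added risk, reduced benefit, or an effect on rights, safety, welfare or data integrity. The same section classes an omitted routine safety test, after earlier normal values, as a deviation.

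**Conclusion.** The point holds for magnesium and phosphate. Two of the four electrolyte disorders named in Section 4.4 have no scheduled measurement at baseline or on treatment, and the only explicit magnesium test is reactive. If the listed single-agent rates applied to this trial, about 7 to 13 of 27 patients would have hypophosphatemia and about 5 to 8 hypomagnesemia at some grade, so these are not rare events. How many would go undetected, and how many would reach grade 3 or higher, cannot be derived from the documents. The effect on the grade 3-5 adverse-event endpoint is therefore unquantified and could be small. The expected direction is undercounting.

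The footnote is a clarity defect on its Week 3, 6 and 9 timing, and a real inconsistency on the interval that follows. Neither finding bears on how PFS-6 is defined or tested. The conclusion rests on reading 5.1.11, 5.3.1 and 5.5 as the complete schedule of required laboratory tests; nothing else in the protocol schedules either assay.

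**What to change.** 1. Reconcile Section 4.4 with Sections 5.1.11 and 5.5 by adding magnesium and phosphate to the chemistry panel at baseline, Cycle 1 Day 1 and each cycle. Blood is already drawn at these visits, so the cost is two routine assays per visit and no extra attendance.
2. Rewrite the triple-asterisk footnote to state study days or cycle numbers, so that it is clear whether Weeks 3, 6 and 9 mean Days 22, 43 and 64 or Days 15, 36 and 57.
3. Reconcile the 4-6 week interval with Section 5.3.1 (pregnancy test where applicable, and serum chemistries, before every cycle) and with Section 5.1.11 (thyroid and coagulation tests listed within serum chemistries). The sponsor should choose the intended frequency and state it identically in all three places.

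Items 2 and 3 are text changes only.
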